#### Bayesian two-parameter logistic model

Upon completion of the DLT observation period of each cohort, summary statistics of the posterior probability distribution of the true DLT rate (2.5%, 25%, 50%, 75%, and 97.5% quantiles) for each predefined dose level will be updated and estimated according to the logistic model. Using data from all subjects completing the DLT period or experiencing a DLT during this period at the completion of a new cohort (and data from all previous cohorts: DE analysis set), the Bayesian logistic model provides a recommended dose level for the next cohort.

Recommendation is based on a loss function (probabilities of being in 1 of the 4 intervals will be multiplied with a loss term as follows:

$0 * P(\text{target dosing (estimated DLT rate in (0.17-0.35])}) + 1 * P(\text{for over dosing (estimated DLT rate in (0.35-0.67]) or under dosing (estimated DLT rate in [0-0.17])}) + 2 * P(\text{excessive dosing (estimated DLT rate in (0.67-1])})$ .

In addition, only doses with estimated probability of  $\leq 25\%$  that the true DLT rate is more than 35% (overdose control) will be recommended by the model. The recommended dose level resulting from the model for the next cohort is the dose with the lowest loss function from all doses fulfilling the overdose control rule. This Bayesian escalation approach will be used to assist the SMC to select the next dose from a predicted set of acceptable doses, i.e., 100 mg, 200 mg, 400 mg, 600 mg, 800 mg and 900 mg BID. It is possible to choose a dose(s) not within the pre-specified dose-escalation plan. Using a Bayesian model-based design aids the SMC in dosing decisions by providing more information compared to a 3+3 design (e.g., an estimated dose-toxicity curve with confidence information utilizing data on all subjects in DE analysis set at time of analysis).

The model will continue to be updated at each SMC until the SMC has decided to stop dose escalation.

Prior distribution and likelihood are used to calculate the posterior probabilities based on Bayes theorem.

The likelihood is defined based on a binomial distribution, modelling the rate of subjects with at least 1 DLT.

The prior distribution is set-up as follows:

The relationship between dose and toxicity rate is defined by

$$P(DLT|d_j, \alpha, \beta) = \frac{\exp\left(\alpha + \exp(\beta) * \log\left(\frac{d_j}{d_{ref}}\right)\right)}{1 + \exp\left(\alpha + \exp(\beta) * \log\left(\frac{d_j}{d_{ref}}\right)\right)}$$

Where  $d_j \in \{100 \text{ mg}, 200 \text{ mg}, 400 \text{ mg}, 600 \text{ mg}, 800 \text{ mg}, 900 \text{ mg}\}$  (or different) and  $(\alpha, \beta)$  are bivariate normally distributed.

Assuming a target toxicity rate of 31 % at a reference dose of 900 mg and a toxicity of 11% at a dose of 400 mg the following could be derived:

$$E(\alpha) = \log(0.31/0.69) = -0.8001$$

$$E(\beta) = \log((\log(0.11/0.89) - \log(0.31/0.69)) / \log(400/900)) = 0.4647$$

Variances are chosen as follows:  $\text{Var}(\alpha) = 1.5^2$ ,  $\text{Var}(\beta) = 1.5^2$ ,  $\text{Cov}(\alpha, \beta) = 0$

The prior distribution has not been changed compared to the protocol defined.

Exemplary code for the update of the prior in R using package bcrm:

```
library(bcrm)

## Pre-defined doses
dose<-c(100,200,400,600,800,900)

## Target toxicity level
target.tox<-0.30

## Toxicity cut-points
tox.cutpoints<-c(0.17,0.35,0.67)

## Losses associated with toxicity intervals [0,0.17]=1, (0.17,0.35]=0, (0.35,0.67]=1, (0.67,1]=2
loss<-c(1,0,1,2)

## definition of prior #####
sdose<-log(dose/900)
mu<-c(log(0.31/0.69),log((log(0.11/0.89)-log(0.31/0.69))/log(400/900)))

Sigma<-rbind(c(1.5^2,0),c(0,1.5^2))
```

```
####following lines: example input of observed data, line needs adjustment according to subject number,  
doses and DLTs observed, I put example scenarios #####;  
data1<-data.frame(patient=1:3,dose=c(rep(1,3)),tox=c(rep(0,3)))  
data2<-data.frame(patient=1:6,dose=c(rep(1,3),rep(2,3)),tox=c(rep(0,6)))  
data3<-data.frame(patient=1:6,dose=c(rep(1,3),rep(2,3)),tox=c(rep(0,5),1))  
data4<-data.frame(patient=1:9,dose=c(rep(1,3),rep(2,3),rep(3,3)), tox=c(rep(0,9)))  
  
##### example modeling step, nmax needs adjustment #####;  
TwoPL logistic.tox.intervals.bcrm<-  
bcrm(stop=list(nmax=3),data=data1,sdose=sdose,dose=dose,ff="logit2",prior.alpha=list(4,mu,Sigma),target.tox=target.tox,constrain=FALSE,tox.cutpoints=tox.cutpoints,loss=loss,method="rjags",burnin.itr=100000,production.itr=1000000)  
print(TwoPL logistic.tox.intervals.bcrm)  
plot(TwoPL logistic.tox.intervals.bcrm)  
  
TwoPL logistic.tox.intervals.bcrm<-  
bcrm(stop=list(nmax=6),data=data2,sdose=sdose,dose=dose,ff="logit2",prior.alpha=list(4,mu,Sigma),target.tox=target.tox,constrain=FALSE,tox.cutpoints=tox.cutpoints,loss=loss,method="rjags",burnin.itr=100000,production.itr=1000000)  
print(TwoPL logistic.tox.intervals.bcrm)  
plot(TwoPL logistic.tox.intervals.bcrm)  
  
TwoPL logistic.tox.intervals.bcrm<-  
bcrm(stop=list(nmax=6),data=data3,sdose=sdose,dose=dose,ff="logit2",prior.alpha=list(4,mu,Sigma),target.tox=target.tox,constrain=FALSE,tox.cutpoints=tox.cutpoints,loss=loss,method="rjags",burnin.itr=100000,production.itr=1000000)  
print(TwoPL logistic.tox.intervals.bcrm)  
plot(TwoPL logistic.tox.intervals.bcrm)  
  
TwoPL logistic.tox.intervals.bcrm<-  
bcrm(stop=list(nmax=9),data=data4,sdose=sdose,dose=dose,ff="logit2",prior.alpha=list(4,mu,Sigma),target.tox=target.tox,constrain=FALSE,tox.cutpoints=tox.cutpoints,loss=loss,method="rjags",burnin.itr=100000,production.itr=1000000)  
print(TwoPL logistic.tox.intervals.bcrm)  
plot(TwoPL logistic.tox.intervals.bcrm)  
  
sessionInfo()
```

Analyses done with R package bcrm (reference to Sweeting, 2013 to be included) or package crmpack will be repeated with East for validation of results.

## 16.2 Secondary Endpoint Analyses

### 16.2.1 M4112 Concentration and Pharmacokinetic Analyses

Available individual M4112 plasma concentrations will be summarized by dose, study day and collection time and presented as summary tables, including summary statistics where data allows. Individual as well as mean concentration-time profiles will be plotted on linear and log scales.

For M4112, PK parameters, as described in the protocol, will be calculated using commercial software (Phoenix® WinNonlin®) following global Merck standard procedures. Nominal collection times may be used for PK determinations in support of the SMC review. Key PK

parameters (Cmax, AUC0-8, Cmin [predose on Day 8, Day 15 and/or Day 1, Cycle 2 as available], and corresponding dose-normalized parameters) will be plotted by dose and study day (individual and mean)

**16.3                    Other Endpoint Analyses**

CCI

CCI

17

## Safety Evaluation

The primary endpoints of this trial are safety-related, and analyses are described in section 16.1.

Safety analyses will be performed on the SAF Analysis Set (unless otherwise specified). All safety parameters will be summarized, by dose level and overall within each treatment arm, unless otherwise stated.

### 17.1 Adverse Events

The severity of adverse events will be graded using the NCI-CTCAE version 4.03, except where CTCAE grades are missing. No imputation of missing grades will be performed. Adverse events will be coded according to the latest MedDRA version at the time of the data cut-off.

- **TEAEs:** Any AEs that are reported (serious and non-serious) will be considered treatment emergent adverse events (TEAEs), with the exception of those that started prior to the first dose of study treatment (unless a worsening of the event is recorded after the first dosing, in which case the event will be counted as a TEAE), or AEs starting more than 30 days after the last dose of study treatment.
- **Related Adverse Events:** AEs with relationship to study treatment of 'Related' reported by the investigator, as well as those of unknown relationship (i.e., no answer to the question, 'Relationship with study treatment'). Relationship is judged separately for M4112, CCI
- **SAEs:** Serious adverse events (as recorded on the AE eCRF page, Serious Adverse Event = 'Yes').
- **AEs Leading to Treatment Discontinuation:** AEs leading to permanent discontinuation of study treatment (as recorded on the AE eCRF page, Action taken with study treatment = 'Drug withdrawn'). Treatment discontinuation is recorded separately for M4112, CCI CCI
- **AEs Leading to Death:** AEs leading to death (as recorded on the AE eCRF page, Outcome = 'Fatal').

AEs will be summarized by MedDRA PT as event category and MedDRA primary SOC as summary category. In general, each subject will be counted only once within each PT or SOC.

AEs with missing classifications regarding relationship to study treatment, and those with start date on or after the start of study treatment, will be considered as related to the study treatment.

Incomplete AE-related dates will be handled as follows:

- If the onset date is missing completely or missing partially – but the onset month and year, or year, are equal to that of the study treatment start – then the onset date will be replaced by the minimum of the start of study treatment and the AE resolution date.
- In all other cases, the missing onset day or month will be replaced by 1.
- Incomplete stop dates will be replaced by the last day of the month (if only day is missing), if not resulting in a date later than the date of subject's death or data cut-off. In the latter case, the date of death or data cut-off will be used to complete the stop date.
- In all other cases the incomplete stop date will not be imputed. If the stop date of an AE is after the date of cut-off, the outcome of the AE is ongoing at cut-off.
- Further information after cut-off (such as fatal outcome) might be taken from the Safety database and reported separately.

All AE tables will be restricted to TEAEs only. The AE tables will include the number and percentage of subjects with at least one TEAE, by MedDRA SOC and PT (both sorted alphabetically), unless otherwise stated.

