## Adverse Events

All AEs will be coded according to MedDRA. Severity of AEs will be graded using the NCI-CTCAE 4.03 toxicity grading scale.

AEs will be summarized according to MedDRA System Organ Classes (SOCs) and Preferred Terms. The incidence of the following will be analyzed:

- TEAEs and SAEs
- TEAEs and SAEs related to study treatment
- TEAEs with CTCAE Grade  $\geq 3$
- TEAEs with CTCAE Grade  $\geq 3$  related to study treatment
- TEAEs leading to withdrawal, dose modifications, temporary and permanent interruptions of study drug, and death.

AESIs will be summarized according to MedDRA SOCs and Preferred Terms.

Of note, missing classifications concerning relationships with study treatment will be considered related to the study treatment.

Subjects who terminated treatment will be summarized by primary withdrawal reason by dose level.

All deaths after first dose of study treatment as well as reasons for death will be tabulated.

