### 17.1.1 All Adverse Events

All AEs will be tabulated in an overall summary table for each treatment arm, to include:

- Any TEAE
- TEAEs leading to death
- Serious TEAEs
- TEAEs, grade  $\geq 3$
- TEAEs leading to permanent treatment discontinuation of M4112
- TEAEs leading to dose reduction of M4112
- AESIs
- Related to M4112 TEAEs
- Related to M4112 TEAEs, grade  $\geq 3$
- Related to M4112 serious TEAEs
- Related to M4112 TEAEs leading to death
- Related to M4112 TEAEs leading to permanent treatment discontinuation of M4112

- Related to M4112 TEAEs leading to dose reduction of M4112

CCI

- CCI [REDACTED]

A listing of all TEAEs will be provided, split into those occurring within the first and after the first cycle. This listing will be sorted by dose level and subject. This listing will additionally contain SOC, PT, grade, SAE (yes/no), DLT (yes/no), relatedness to M4112 (yes/no), CCI [REDACTED] (yes/no), to CCI [REDACTED] (yes/no), start date (+treatment day), stop date (+treatment day), and outcome. This listing is to be produced on the current cut-off in JReview.

Additionally, a listing of all adverse events grade  $\geq 3$  will be provided, sorted by SOC and PT within each dose level and subject. These will also include seriousness, dose level, time since last and since first administration of study drug, age, sex, and race of the subject) and relatedness to M4112 (yes/no), CCI [REDACTED] (yes/no), to CCI [REDACTED] (yes/no). This listing is to be produced on the current cut-off in JReview.

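### SMC iAP 17.1 contradicts itself on related adverse events: one sentence, read literally, also makes every event with onset on or after first dose related

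*SAP*

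**What the plan says.** The SMC iAP (version 1.0, 30 January 2018, appended to the final IAP) gives two rules on relationship in Section 17.1.

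- The bullet defining related adverse events takes in "AEs with relationship to study treatment of 'Related' reported by the investigator, as well as those of unknown relationship", the latter being events for which the relationship question was not answered. Onset date plays no part.
- Lower down, just before the date-imputation rules, a sentence opens "AEs with missing classifications regarding relationship to study treatment, and those with start date on or after the start of study treatment, will be considered"; its closing words class both groups as treatment-related.

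The other documents side with the bullet. Protocol 8.5.6 says "Of note, missing classifications concerning relationships with study treatment will be considered related to the study treatment". Final IAP 15.2 counts events the Investigator reported as related, or of unknown relationship, with no start-date condition. Section 9 of the SMC iAP declares no changes from the protocol's planned analyses.

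Three further provisions decide what the second rule would do:

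- An event that began before dosing is not treatment-emergent "unless a worsening of the event is recorded after the first dosing, in which case the event will be counted as a TEAE".
- "All AE tables will be restricted to TEAEs only", and the tables count subjects with at least one TEAE.
- Section 17.1.1 pairs all-causality rows with related rows, for example "Related to M4112 serious TEAEs".

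**The concern.** In the second rule the words *and those* open a new group. They do not narrow the group with a missing relationship. As printed, any event with onset on treatment becomes related whatever the Investigator recorded. Protocol 7.4.1.1 requires Investigators to assess causality systematically, and this sentence would override the result. It sits beside the date-imputation rules and reads as an instruction to the programmer.

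Treatment-related events are part of a primary endpoint (Protocol 8.3.1, repeated in SMC iAP Section 6), and the SMC weighs events beyond Cycle 1 DLTs when it advises on dose (Protocol 5.1 and 6.2.4). In advanced cancer many on-treatment events may come from the disease, and the related rows are there to set those apart. A flag that is nearly always positive would remove that contrast, and it errs in one direction only, towards overstating drug-related toxicity.

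**Working it through.** The plan states no figure to reproduce. The check is an enumeration of cases, followed by one line of arithmetic.

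**Step 1. Cases.** A TEAE either starts on or after first dose, or starts before it and worsens. The relationship is Related, Unrelated or missing. That gives 2 × 3 = 6 cases. The last column shows a possible rewording: missing relationship *and* onset on or after first dose, plus those the Investigator called related.

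| Onset | Relationship | All-causality row | Bullet, Protocol 8.5.6, final IAP 15.2 | Literal sentence plus bullet | Missing *and* on/after onset, plus Related |
|---|---|---|---|---|---|
| On/after first dose | Related | in | in | in | in |
| On/after first dose | Unrelated | in | out | **in** | out |
| On/after first dose | Missing | in | in | in | in |
| Before, worsened | Related | in | in | in | in |
| Before, worsened | Unrelated | in | out | out | out |
| Before, worsened | Missing | in | in | in | **out** |
| **Cases counted** | | 6 of 6 | 4 of 6 | 5 of 6 | 3 of 6 |

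The literal sentence differs from the definition in one case: onset on treatment, judged unrelated. It differs from the all-causality row in one case: onset before dosing, worsened, judged unrelated.

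**Step 2. Date imputation.** Under Section 17.1, an onset date that is wholly missing, or partial but matching the month and year (or the year) of treatment start, is set to the earlier of treatment start and resolution. Such events will usually land on the first day of treatment, inside the start-date clause.

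**Step 3. Rows affected.** Section 17.1.1 shows 13 readable rows: seven all-causality (any, death, serious, grade 3 or higher, permanent discontinuation, dose reduction, AESI) and six related to M4112, mirroring all of these except AESI. The list continues into redacted text, so 13 is the number of readable rows and not the known size of the table.

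**Step 4. Size in a column.** If k subjects among n are wrongly counted in a row, the percentage rises by 100 × k/n.

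- Dose-level column, n = 3 (the planned cohort size), k = 1: 100 × 1/3 = 33 points.
- Overall column, n = 6 (the fewest treated subjects in an arm at which summary outputs are produced, SMC iAP Section 8.1), k = 1: 100 × 1/6 = 17 points.

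A subject is wrongly counted only if no other event of theirs already puts them in that row as related.

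**The case against.** The strongest reply is that the section already holds the right rule. The bullet is the formal definition, the protocol and final IAP agree with it, and no change from the protocol is declared. A careful programmer would probably take the later sentence to mean a missing relationship with onset on treatment, or ignore it. The practical reach is also limited: the final IAP was written after the decision to stop the study early, and its own rule is sound.

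All of that stands as a limit on size. It does not settle which of two printed rules the SMC programs followed.

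A reader might infer four stronger things that the documents do not support:

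- *That the SMC iAP simply defines all on-treatment events as related.* It does not. It gives two conflicting rules.
- *That related rows would equal all-causality rows exactly.* Events that began before dosing, worsened and were judged unrelated stay out.
- *That each misread event adds 33 points.* The tables count subjects, so an extra event in a subject already counted changes nothing.
- *That dose recommendations were distorted.* The Bayesian model takes DLTs (SMC iAP 16.1). Some DLT criteria in Protocol 6.2.4 involve attribution to study drug, but no text ties them to this derived flag. The SMC also receives Patient Profiles built from raw data (Section 8). The adverse event listings carry a yes/no relatedness field, and the plan does not say whether it holds the Investigator's answer or the derived value.

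**Conclusion.** The contradiction is real, and the later sentence is wrong as written. Followed literally, it moves every on-treatment event judged unrelated into the related count and leaves the six readable related rows close to copies of their all-causality rows. The overstatement is 33 percentage points for each subject wrongly counted in a three-subject dose-level column.

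This size is conditional on literal programming, which the documents neither show nor rule out, and on a three-subject column. The effect shown is confined to the derived SMC summary rows. The final analysis uses the consistent definition. The point should be corrected because the text is an operative rule and the repair is small; it gives no ground for saying that any escalation decision was wrong.

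**What to change.** In SMC iAP 17.1, delete the start-date clause, so that the sentence says only that adverse events with a missing relationship to study treatment are considered related. It then agrees with the bullet, Protocol 8.5.6 and final IAP 15.2.

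Rewording it as missing relationship *and* onset on or after first dose is not a safe substitute. As the last column of the table shows, an event that began before dosing, worsened on treatment and has no recorded relationship would then not be imputed as related, contrary to all three definitions.

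Then check how the related flag was derived in every SMC output already produced, including the source of the yes/no field in the listings, and record the result. The cost is one clause and a program check, with affected tables rerun only if the literal rule was used.

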### 17.1.1 All Adverse Events

All AEs will be tabulated in an overall summary table for each treatment arm, to include:

- Any TEAE
- TEAEs leading to death
- Serious TEAEs
- TEAEs, grade  $\geq 3$
- TEAEs leading to permanent treatment discontinuation of M4112
- TEAEs leading to dose reduction of M4112
- AESIs
- Related to M4112 TEAEs
- Related to M4112 TEAEs, grade  $\geq 3$
- Related to M4112 serious TEAEs
- Related to M4112 TEAEs leading to death
- Related to M4112 TEAEs leading to permanent treatment discontinuation of M4112

- Related to M4112 TEAEs leading to dose reduction of M4112

CCI

- CCI [REDACTED]

A listing of all TEAEs will be provided, split into those occurring within the first and after the first cycle. This listing will be sorted by dose level and subject. This listing will additionally contain SOC, PT, grade, SAE (yes/no), DLT (yes/no), relatedness to M4112 (yes/no), CCI [REDACTED] (yes/no), to CCI [REDACTED] (yes/no), start date (+treatment day), stop date (+treatment day), and outcome. This listing is to be produced on the current cut-off in JReview.

Additionally, a listing of all adverse events grade  $\geq 3$  will be provided, sorted by SOC and PT within each dose level and subject. These will also include seriousness, dose level, time since last and since first administration of study drug, age, sex, and race of the subject) and relatedness to M4112 (yes/no), CCI [REDACTED] (yes/no), to CCI [REDACTED] (yes/no). This listing is to be produced on the current cut-off in JReview.

### 17.1.2 Adverse Events Leading to Treatment Discontinuation

A listing of TEAEs leading to treatment discontinuation, interruption, or dose reduction of each study drug will be provided. This listing, sorted by SOC and PT, will include: AE, SOC, PT, relationship to M4112, CCI [REDACTED], and CCI [REDACTED] (as applicable), seriousness, treatment discontinuation for M4112, CCI [REDACTED], and CCI [REDACTED] (as applicable), dosing cohort, time since last and since first administration of M4112, and subject's age, sex, and race.

## **17.2 Deaths, Other Serious Adverse Events, and Other Significant Adverse Events**

### **17.2.1 Serious Adverse Events**

A listing of all SAEs will be provided, sorted by SOC and PT, including: AE, SOC, PT, relationship to M4112, **CCI** and **CCI** (as applicable), dosing cohort, time since last and since first administration of M4112, and subject's age, sex, and race.

### **17.2.2 Adverse Events of Special Interest**

A listing of all AESIs will be provided, sorted by SOC and PT, including: AE, SOC, PT, relationship to M4112, **CCI** and **CCI** (as applicable), dosing cohort, time since last and since first administration of M4112, and subject's age, sex, and race.

## **17.3 Clinical Laboratory Evaluation**

The severity of laboratory results for hematology and chemistry parameters will be graded according to the NCI-CTCAE version 4.03.

All clinical laboratory analyses will be performed on the SAF Analysis Set.

### **Hepatotoxicity assessment**

A plot of peak ALT versus peak total bilirubin, both relative to the ULN, will be provided. This eDISH (evaluation of drug-induced serious hepatotoxicity) plot will have reference lines at 3xULN for ALT and 2xULN for total bilirubin. Each subject will get a special character/color combination; the color will represent dose level, and the characters within each color will be used to distinguish the subjects from one another, with ID numbers presented in a legend (sorted by dose level and subject ID number).

